The effectiveness of single session 20-minute mindful breathing in symptom control in kidney transplant recipients: a randomised controlled trial

Version 1.0

Date 4/11/2020

Introduction

Therapeutic mindfulness is the practice of being aware of the present moment¹. Previous studies have suggested benefit of mindfulness-based therapy for improving general health conditions. The body of evidence to date included both clinical trials, as well as observational and qualitative studies showing evidence of benefit^{2, 3, 4}. While the majority of outcomes measured involved improvement in psychological well-being, a few other measured outcomes includes looking at physiological changes in response to mindfulness-based therapy⁵. The scope of study participants were wide, with involvement of healthy volunteers to palliative care patients, as well as patient caregivers. However, a new perspective of study is worth discovering based on population of kidney transplant recipients suffer from varying degree of symptoms. From our literature review, two RCTs were identified which have reported positive association in psychosocial symptoms reduction through mindfulness-based interventions among solid organ transplant recipients^{6, 7}. Both studies involved multiple sessions of mindfulness-based intervention and long-term outcome measurement.

In this study, we aim to study the effectiveness of single session 20-minute mindful breathing in symptom control in kidney transplant recipients. Results from this study will help clinicians to manage patients for better symptom control, by offering multi-modality approaches in future patient care, more so in patients who prefer non-pharmacological interventions or are experiencing side effects of the pharmacological management.

Objectives

To study the effectiveness of single session 20-minute mindful breathing in symptom control in kidney transplant recipients.

Methodology

A randomized controlled trial was conducted in renal transplant clinic of a tertiary center. A total of 192 adult kidney transplant recipients (KTR) attending renal transplant clinic were screened for eligibility. Subjects who aged \geq 18-year-old, scored \geq 4 in at least 1 symptom at 0-minute based on Edmonton Symptom Assessment System (ESAS), and consented to participate were being recruited. Subjects with underlying psychiatric comorbidities and who were not able to communicate were excluded. A total of 60 subjects were randomized equally into control and intervention arms by electronic number randomizer. Subjects in control arm received only standard care. Subjects in intervention arm received a single session 20-minute guided mindful breathing session in addition to standard care. Subjects in both arms were requested to rate their symptoms using ESAS at 20-minute. Data collected were analyzed using SPSS version 21.

Ethics

Medical ethic approval was obtained from the medical ethic committee of University Malaya Medical Center. Informed consent was obtained from all the subjects of the study. The study was conducted according to the Good Clinical Practice (GCP) guideline.

Intervention

Intervention involves a single session 20-minute mindful breathing guided by the investigator using a uniform script (as below). Subjects in the control group will be told to continue with their activities for 20 minutes.

Step 1 (5 minutes): Identifying the in- breath and outbreath

Make yourself comfortable. Relax your body. Close your eyes gently. Take two deep breaths slowly. Then, breathe naturally. Notice the flow of air through your nose. Rest your attention gently on the breath. Breathing in, you know you are breathing in. Breathing out, you know you are breathing out. In – out, in – out, in – out. If you are distracted by any sounds, body sensations, thoughts or feelings, gently come back to your breath. Be aware of your in-breath and outbreath for the next few minutes.

Step 2 (5 minutes): Following the entire length of the breath

Continue to relax your body with your eyes closed. Continue to pay attention to your breath. Follow the entire length of your breath. Follow the beginning, the middle and the end of your in- breath, and the beginning, middle and the end of your out-breath. If you are breathing in a long breath, you know you are breathing in a long breath. If you are breathing in a short breath, you know you are breathing in a short breath. If you are breathing out a long breath, you know you are breathing out a long breath. If you are breathing out a short breath, you know you are breathing out a short breath. Do not force yourself to take a long or short breath. Just breathe naturally. Be aware of the entire length of the breath. In – in – in, out – out – out, in – in – in, out – out – out. If you are distracted by any sounds, body sensations, thoughts or feelings, gently come back to your breath. Follow the entire length of your breath for the next few minutes.

Step 3 (5 minutes): Bringing the mind back to the body

As you follow the entire length of your breath, bring your mind back to your body. Instead of thinking about the past or future, bring your mind back to now. Bring your mind and body together as one. As you breathe in, feel your whole body moving with your breathing in. As you breathe out, feel your whole body moving with your breathing out. Breathing in, you are aware of your whole body as you are breathing in. Breathing out, you are aware of your whole body as you are breathing out. Feel the different parts of your body as you breathe in and out. Then, feel the body as a whole, fully united with your mind. Feel the wholeness of yourself with each breath for the next few minutes.

Step 4 (5 minutes): Relaxing the body

Once your breathing is harmonious, your body will relax naturally. Feel whether there is any tension in your body. Breathe and relax the tension one by one, from the top to the bottom. Relax your head, face, neck, arms, forearms, hands, chest, abdomen, legs, feet. Then relax your whole body all at once. Breathing in, you calm your body when you are breathing in. Breathing out, you smile. Again, breathing in, you calm your body when you are breathing in. Breathing out, you smile. In – out – calm – smile, in – out – calm – smile, in – out – calm – smile. Feel your breath flowing through your body and calming your body. Feel your breath leaving your body and smile. Continue to relax your whole body for the next few minutes

Outcome measured

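### Does the objective need a time frame, given that symptoms are rated only once after baseline, at 20 minutes?

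*Combined protocol and SAP*

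**What the plan says.** The Objectives section has a single sentence, whose core is "to study the effectiveness of single session 20-minute mindful breathing in symptom control in kidney transplant recipients". The title and the aim in the Introduction share the phrase. In all three, the 20 minutes describe the length of the session, not the time of the outcome.

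The timing is in the Methodology section. Eligibility rests on a score of at least 4 on one or more ESAS symptoms at 0-minute. After randomisation, "Subjects in both arms were requested to rate their symptoms using ESAS at 20-minute". No other rating time appears anywhere, and the Outcome measured section holds only the ESAS form.

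The Intervention section reads: "Intervention involves a single session 20-minute mindful breathing guided by the investigator using a uniform script". Control subjects carry on with their activities for the same 20 minutes.

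Two sentences in the Introduction bear on scope. On the two earlier trials in solid organ transplant recipients: "Both studies involved multiple sessions of mindfulness-based intervention and long-term outcome measurement". On the use of the findings: "Results from this study will help clinicians to manage patients for better symptom control, by offering multi-modality approaches in future patient care".

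**The concern.** An objective that speaks of symptom control without a time limit can be read as covering relief that lasts. The data cannot speak to that, because the only rating after baseline comes nominally as the session closes. The last step of the script is itself guided relaxation, so the rating would catch subjects at about their most relaxed. The Introduction then ties the results to later patient care, including patients who prefer non-drug options or have side effects from drugs, and for them the duration of relief matters.

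If a report simply repeated the objective as its conclusion, it would claim more than was measured. The possible harm is over-generalisation. The randomised comparison at 20 minutes would still be valid.

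**Working it through.** **Inputs from the document.** Session length 20 minutes (Intervention); four scripted steps of 5 minutes each (Intervention); ESAS at 0-minute and 20-minute (Methodology); control period 20 minutes (Intervention); 60 subjects split equally (Methodology), so 60 / 2 = 30 per arm.

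**1. Session length.** 4 x 5 = 20 minutes, which reproduces the stated length.

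**2. Lag from end of session to outcome.** If the clock starts with the session, 20 - 20 = 0 minutes. If g minutes of consent, randomisation or set-up come between the 0-minute rating and the start, the session ends at 20 + g and the lag is 20 - (20 + g) = -g. The document does not say which clock applies. Either way, no planned rating falls after the nominal end of the session.

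**3. Ratings per subject.** One after baseline; none after 20-minute, for all 60 subjects.

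**4. Does the text claim more than this?** Set side by side:

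- Objective: effect on symptom control, no time given.
- Methodology: the ESAS time, given plainly for both arms.
- Introduction, earlier trials: "Both studies involved multiple sessions of mindfulness-based intervention and long-term outcome measurement". A single session rated at 20 minutes is the evident contrast, although the text does not spell it out.
- Introduction, use of results: this says that clinicians may offer the option in future. It does not say how long relief lasts.

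No sentence states or implies persistence.

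**5. What would rewording change?** The sample size, the arms, the rating and the comparison would all stay as they are, so the numerical effect is nil.

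**6. Would a later rating be worth adding?** The document gives no SD, effect size, alpha or missing-data rate, so the figures here are assumptions: two-sided 5% t-test, item SD of 2 to 3 points, immediate difference of 0.8 or 0.5 SD, half of it remaining later.

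- Half-width of the 95% CI in SD units = t(0.975, 2n - 2) x sqrt(2/n). At n = 30: 2.002 x 0.258 = 0.517. With 10% missing (n = 27): 2.007 x 0.272 = 0.546. With 20% missing (n = 24): 2.013 x 0.289 = 0.581.
- In ESAS points at n = 30: 0.517 x 2 = 1.03 to 0.517 x 3 = 1.55.
- Power at n = 30 (noncentral t): 33% for 0.8 / 2 = 0.4 SD and 16% for 0.5 / 2 = 0.25 SD. A non-significant later result would then occur 100 - 33 = 67% or 100 - 16 = 84% of the time.
- Difference detectable with 80% power: 0.74 SD at n = 30, 0.78 at n = 27, 0.83 at n = 24.

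So a later rating would often fail to separate fading from persistence. These figures describe that extra rating only; they do not measure a defect in the plan.

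**The case for a change.** The strongest case for a change is that conclusions tend to echo objectives, and here the title, aim and objective all omit the time. The Outcome measured section does not supply it, and the contrast with long-term trials is never completed by a statement that this trial looks only at an immediate effect. Stating the time would cost nothing except a narrower claim, and could be done even with data collection closed.

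The facts in this stand. What fails is the step to a needed change. A general objective with its timing in the methods is ordinary drafting, and in a document this short the 20-minute rating is hard to miss. The harm depends on a conclusion that the document does not contain. Relief at 20 minutes is also a form of symptom control, so the objective is broad but not false.

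The obvious rewording has a weakness of its own. Saying that symptoms were rated at the end of the session asserts something the document does not establish, because 0-minute is attached to the eligibility score and the session start is not placed on that clock. The undefined time zero is a real gap, but a separate one: wherever zero lies, the comparison remains short-term.

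A later rating would be the only substantive change, and it appears to be out of reach. Apart from the control instruction, the account of screening, randomisation, rating and analysis is in the past tense. Its timing would also be arbitrary, and clinic events between the two ratings could blur it.

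**Conclusion.** The observation is accurate, but it calls for no change to the plan. The title, aim and objective carry no time frame. The Methodology section does, and it fixes what the trial can show: a between-arm difference in ESAS at 20 minutes, with the duration of any difference unknown. An analyst working from the Methodology section would report exactly that. The effect on any estimate, test or sample size is zero.

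This rests on three readings. The 20-minute rating was the only one after baseline, as the text indicates. Collection is finished, as the past tense suggests. The report describes the result as a 20-minute one and not as lasting relief. If a report did claim persistence, the criticism would belong to that report, since nothing in this document makes the claim.

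### Does a symptom rating at 20 minutes leave no time for randomisation and set-up before a 20-minute session?

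*Combined protocol and SAP*

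**What the plan says.** Four statements in the combined protocol and SAP bear on timing.

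- **Entry (Methodology).** Subjects need a score of at least 4 "in at least 1 symptom at 0-minute based on Edmonton Symptom Assessment System (ESAS), and consented to participate were being recruited". The minute-0 ESAS is therefore the eligibility filter.
- **Allocation (Methodology).** 192 recipients were screened, and "A total of 60 subjects were randomized equally into control and intervention arms by electronic number randomizer". Since entry depends on the ESAS score, allocation comes after it.
- **The 20 minutes (Intervention).** The intervention arm is guided through a uniform script of four steps, each marked as 5 minutes. For the other arm, "Subjects in the control group will be told to continue with their activities for 20 minutes".
- **Outcome rating (Methodology).** "Subjects in both arms were requested to rate their symptoms using ESAS at 20-minute".

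No section names the event that starts the 20 minutes, describes a second baseline ESAS, or gives a window for the later rating. The short horizon is deliberate. The Introduction contrasts this trial with two earlier ones: "Both studies involved multiple sessions of mindfulness-based intervention and long-term outcome measurement". Nowhere is lasting relief claimed.

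**The concern.** Read literally, minute 0 and minute 20 are points on one clock that starts when the entry ESAS is completed. Scoring the form, randomising and settling the subject must come next, followed by a session that by itself fills 20 minutes. Any set-up time then makes it impossible for the second rating to be both 20 minutes after the first and at the end of the session.

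If that were the real procedure, one of two things would follow. Either the intervention arm was rated before the script ended, so that a part-delivered session was compared with control, or the arms were rated at different times since baseline. Analysis could not remove the second problem, because arm would determine elapsed time. This is the only post-baseline rating described, so every comparison of symptom scores rests on it.

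**Working it through.** **Inputs from the documents.** Entry ESAS at minute 0; four script steps of 5 minutes; control period of 20 minutes; second ESAS at minute 20 in both arms.

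**Assumptions not in the documents.** Set-up time d = 2, 5 or 10 minutes; background drift g = 0.5 or 1.0 points per 20 minutes on a 0–10 item, linear and common to both arms.

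**Step 1. Session length.** 4 × 5 = 20 minutes, which agrees with the stated length.

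**Step 2. Slack on a single literal clock.** 20 (second rating) − 0 (entry ESAS) − 20 (session) = 0 minutes. The arithmetic is right, but it depends on the clock starting at the entry ESAS, and no section says that it does.

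**Step 3. Three possible clocks, set against the text.**

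| Clock | Consequence | Fit with the text |
|---|---|---|
| One clock from the entry ESAS, both arms | Script minutes done at rating = 20 − d: 18, 15 or 10 (90%, 75%, 50%) | Poor. Methodology reports the 20-minute session as received, then gives the rating. The script has eyes closed in Steps 1 and 2, and nothing suggests a form was filled in part-way. |
| Clock starts after allocation, both arms | Both rated at 20 + d minutes: 22, 25 or 30 | Good. The control instruction is specific to that arm, so it can only follow allocation, and it supplies its own 20 minutes. |
| Session end in one arm, 20 minutes from the entry ESAS in the other | 22, 25 or 30 minutes against 20 | Poor. One rating time is given for both arms, and a 20-minute control period begun after allocation does not end 20 minutes after the entry ESAS. |

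The second row is the natural reading: the labels mean before and after a 20-minute period.

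**Step 4. What could remain under the natural reading.** Set-up need not take equally long in both arms; settling someone for a guided session may take longer than telling a control to carry on. If set-up differs by Δ minutes, the shift in the between-arm difference from drift alone is g × Δ / 20.

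- g = 0.5: Δ = 2 gives 0.05; Δ = 5 gives 0.125; Δ = 10 gives 0.25 points.
- g = 1.0: Δ = 2 gives 0.10; Δ = 5 gives 0.25; Δ = 10 gives 0.50 points.

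The third clock in the table gives the same shifts with Δ = d, because the control arm then has no set-up time at all. It is the extreme case of unequal set-up. With equal set-up, Δ = 0 and the shift is zero.

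**The case for a change.** The best case for acting is that the omission is real, concerns the only outcome rating, and would cost a few sentences to close. The intervention arm has a visible anchor in the first line of the script, while the control arm has only an instruction whose timing is not recorded in the plan. A reader cannot prove from the text which clock was used.

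Two parts of this stand. The starting event is indeed unstated, and the interval between the two ratings is 20 minutes plus an unknown set-up time that may not be equal across arms. Calling the timing difference exactly zero would therefore go too far.

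The rest does not carry. The control instruction is itself a usable anchor. The readings that would damage the comparison have to be imposed on a text that points away from them. Writing down the time origin, or tabulating the intervals if clock times exist, would add description but alter no rating, comparison or estimate. Adding the time point to the objective would only repeat what Methodology already states.

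**Conclusion.** The concern does not call for a change. The figure of 0 minutes for set-up comes from reading two nominal labels as one literal clock. Taken together, the Methodology and Intervention sections describe a rating before and a rating after a 20-minute period begun once allocation is known. That schedule is feasible and treats the arms alike.

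What is left is a missing detail that those running and reporting the trial can supply from what was done. Its effect on the comparison is zero if set-up took equally long in both arms. Otherwise it is probably small: 0.05 to 0.25 points for an imbalance of 2 to 10 minutes at a drift of 0.5 points per 20 minutes, and twice that at a drift of 1.0. These sizes rest wholly on assumed set-up times and an assumed linear drift; the documents support no particular value, so the true size and direction cannot be computed from them. The conclusion also rests on the natural reading of the two time labels, which the text favours but does not state outright.

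### The 20 minutes between the two ESAS ratings are scripted in the intervention arm but unstandardised and unrecorded in the control arm, so clinic events can mix with the effect of mindful breathing, in either direction

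*Combined protocol and SAP*

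**What the plan says.** The Methodology section places the trial in a renal transplant clinic, with 60 subjects randomised equally. The ESAS at 0 minutes is both the eligibility rating and the baseline. The outcome rating follows 20 minutes later: "Subjects in both arms were requested to rate their symptoms using ESAS at 20-minute".

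The same section describes the arms as standard care with and without the session. For controls it says "Subjects in control arm received only standard care". For the other arm it says "Subjects in intervention arm received a single session 20-minute guided mindful breathing session in addition to standard care".

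The Intervention section then says how the 20 minutes are spent. The session is guided by the investigator from a uniform script in four steps of 5 minutes, beginning with "Step 1 (5 minutes): Identifying the in- breath and outbreath". Subjects make themselves comfortable and close their eyes, and Step 2 tells them: "Continue to relax your body with your eyes closed". The whole provision for the other arm is "Subjects in the control group will be told to continue with their activities for 20 minutes".

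The plan does not say where controls stay or what they may do. It does not place the window relative to the consultation, tests or waiting. It does not say what happens if a clinic step comes up before the second rating, and it does not ask for such events or the actual rating times to be recorded.

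**The concern.** The outcome is a set of momentary self-ratings, including tiredness, nausea, anxiety, drowsiness, appetite, wellbeing and breathlessness. A consultation, a needle, a walk or a meal could plausibly move several of these within 20 minutes. A subject following a script with eyes closed is unlikely to meet such an event during the window. A control who has been told to carry on may well do so.

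The arms can therefore differ in two respects over the measured interval: the session, and exposure to ordinary clinic events. The second difference arises after allocation, from the control instruction itself, so randomisation does not balance it. It is also separate from the lack of masking, because it would remain if every rating were perfectly candid.

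A needle or bad news among controls would make the session look better than it is. A reassuring consultation or a meal would hide a real benefit. A control who has been called in or has walked off may also be harder to rate on time. With nothing recorded, none of this can be checked afterwards.

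**Working it through.** **Step 1. How much of the interval is fixed in each arm.** The session is 4 steps × 5 minutes = 20 minutes. The rating interval is 20 − 0 = 20 minutes. The script therefore fills the whole interval in the intervention arm. In the control arm the plan specifies 0 of the 20 minutes.

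**Step 2. What the documents give for sizing the effect.** The one usable figure is 60 subjects randomised equally, so 60 / 2 = 30 per arm. The plan states no SD, test, significance level, power or target difference, so the 60 cannot be reproduced. It also gives no share of controls meeting a clinic event and no effect of such an event. The rest of this working is an illustration on assumed inputs.

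**Step 3. Assumptions.** One ESAS item (0 to 10) is compared between arms by a normal-approximation test at two-sided 5%. The item SD is 2. Mindful breathing has no specific effect. A share f of controls meets an event that shifts the item by d points, always in the same direction.

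**Step 4. Formulas.**
- Bias = f × d.
- SE of the difference = 2 × √(2/30) = 0.516.
- Rejection rate = P(|Z + bias/SE| > 1.96).

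| f | d (points) | Bias (points) | Bias / SE | Rejection of a true null |
|---|---|---|---|---|
| 10% | 1 | 0.1 | 0.19 | 5.4% |
| 30% | 1 | 0.3 | 0.58 | 8.9% |
| 50% | 1 | 0.5 | 0.97 | 16.2% |
| 10% | 2 | 0.2 | 0.39 | 6.7% |
| 30% | 2 | 0.6 | 1.16 | 21.3% |
| 50% | 2 | 1.0 | 1.94 | 49.1% |

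**Step 5. Sensitivity.**
- *Extra control variance.* Events in only some controls add d² × f × (1 − f) to the control variance. For f = 30% and d = 2, the control variance is 4 + 4 × 0.3 × 0.7 = 4.84, and the SE becomes √((4 + 4.84)/30) = 0.543. The three 2-point rates fall to about 7%, 20% and 45%.
- *Item SD.* With SD between 1.5 and 2.5, and without the extra variance, the mildest case (f = 10%, d = 1) gives 5.3% to 5.8%. The most severe (f = 50%, d = 2) gives 34% to 73%.
- *Mixed directions.* If 20% of controls are shifted up by 2 and 10% down by 2, the bias is 2 × (0.20 − 0.10) = 0.2 rather than 0.6, and the rate returns to about 7%. An even split of equal shifts gives no bias.

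The effect therefore runs from negligible to large. Nothing in the plan shows where this trial lies.

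**The case against.** The best defence is that the comparison is pragmatic. The objective is worded as effectiveness, and the arms are standard care with and without the session. On that reading, 20 quiet minutes in place of ordinary clinic activity are part of what assignment to the session brings, and randomisation protects the test of that package. This stands for that question, and the rejection rates above do not apply to it. It is only a partial answer. If controls reach clinic steps during the window while intervention subjects have them deferred past the second rating, the session is not simply added to standard care over the interval that is measured. The stated objective also attributes the effect to mindful breathing itself.

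A second objection is that the illustration pushes every affected control the same way on the same item. This also stands: different events act on different items and may cancel. The control instruction can also be read as carrying on with what they were already doing, which may simply be waiting.

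A reader might infer more than the documents support:
- *That intervention subjects are seated, cannot be called away and are always at hand at 20 minutes.* The script says only that they are comfortable, relaxed and with eyes closed. No rule excludes an interruption.
- *That clinic events happened, and in controls only.* The plan neither schedules nor excludes them in either arm. That they would fall mainly among controls is an inference from the two sets of instructions.
- *That the result is biased in favour of the session.* Nothing in the documents fixes the direction.

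**Conclusion.** The point holds as a gap in standardisation and recording. Followed as written, the plan leaves the control window open in a working clinic and fills the same window by script in the other arm. A post-allocation difference in exposure to clinic events is therefore possible and could not be detected afterwards. For a claim about the specific effect of mindful breathing, this confounds the comparison, with unknown direction.

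Its size is not derivable from the documents. With 30 per arm, an assumed item SD of 2, 10% to 50% of controls affected, a shift of 1 or 2 points and all shifts one way, the false-positive rate runs from about 5% to about 49%. It stays near 5% if the shifts cancel. The documents do not show that the upper end applies, or that any published difference is an artefact. The change is cheap and the gap is real, so the sponsor should make it. Confidence that the effect is material is moderate at most.

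**What to change.** Replace the control sentence in the Intervention section with a paragraph along these lines:

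> In both arms the 20 minutes take place at the same fixed point of the visit. Control subjects stay in the waiting area and do what they normally do while waiting. No clinic step is scheduled between the two ESAS ratings in either arm. Any event that does occur between the ratings, and the actual time of each rating, is recorded for every subject.

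The cost is one paragraph, some clinic scheduling, a short record of events and times, and up to 20 minutes of waiting for about 30 controls. No extra subjects are needed. The small downside is that the comparator becomes usual waiting rather than any activity. This does not match the investigator's guidance and attention, so it removes the difference in clinic events but does not isolate breathing from attention.

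The Methodology section is written in the past tense, so recruitment may already be complete. In that case, do not adjust for events in the window. They occur after randomisation and would be largely confined to controls, so adjustment would in effect compare all intervention subjects with a selected, event-free set of controls. The documents also mention no log from which to identify such events. Keep the randomised comparison as primary, describe any events that are known, and limit the conclusion to the session versus unstandardised usual clinic time.
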